10.3 Clinical laboratory evaluations

Hematology, biochemistry, and urinalysis samples will be taken at Screening, Baseline, Weeks 2, 4, 12, 24, 36, 48, 60, 72, 84, and 96/WD Visit. Testing for HBs-Ag, HBc-Ab, HBs-Ab, HCV-Ab, HIV, and HLA-B27 (if not yet known) will be performed at Screening.

The changes from Baseline in laboratory evaluations will be analyzed over time in the SS for observed cases. Shift tables concerning the normal range at each post-baseline visit, will also be produced for each hematology and biochemistry laboratory variable. The shifts will be categorized using L, N, H, missing, and total.

Markedly abnormal laboratory values

The number of subjects with any markedly abnormal hematology or biochemistry value will be tabulated. Values fulfilling the criteria below will be classified as markedly abnormal high (MH) or markedly abnormal low (ML). If no lower (upper) limit is given, the classification ML (MH) is not applicable.

- Hemoglobin < lower limit normal (LLN) and decrease from Baseline >2g/dL
- Hemoglobin <8g/dL
- White blood cells <2000/ μ L
- Lymphocyte count <1000/ μ L
- Neutrophil count <1000/ μ L
- Platelet count <50000/ μ L
- ALT >3x upper limit normal (ULN)
- AST >3x ULN
- ALP >3x ULN
- Bilirubin \geq 2x ULN
- Creatinine >1.8x ULN
- Calcium >12.5mg/dL
- Calcium <7mg/dL
- CK >4x ULN
- Glucose >250mg/dL
- Glucose <40mg/dL
- Potassium >6.4mmol/L
- Potassium <3mmol/L
- Sodium <125mmol/L
- Uric acid \geq 3x ULN

The number of subjects meeting the criteria for Hy's Law is of particular importance. The criteria are as follows:

- \geq 2 x ULN elevation of Bilirubin and 3 x ULN elevation of either ALT or AST

In order to meet the above criteria, a subject must experience the elevation in bilirubin and ALT or AST at the same visit. For example, a subject who experiences a \geq 2 x ULN elevation of bilirubin at one visit and a 3 x ULN elevation in ALT (or AST) at a subsequent visit has not fulfilled the Hy's law criteria.

If a repeat sample is taken, the repeated sample data will be used when possible. If the value of a variable collected at the scheduled visit is missing and an additional sample associated with this

visit is taken before the next scheduled visit, the missing value will be replaced by this value. Early Withdrawal Visits will be assigned to what would have been the next scheduled visit. In the Urinalysis, microscopy (WBC, RBC, casts, crystals, and bacteria) will be performed only when there are abnormalities on the dipstick. This data will be listed and not presented in tables.

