10.3 Adverse events of interest

An AE of interest is any AE that a regulatory authority has mandated be reported on an reions of variations thereof expedited basis, regardless of the seriousness, expectedness, or relatedness of the AE to the administration of a UCB product/compound.

Adverse events of interest include:

- Serious infections including opportunistic infections
- Malignancies including lymphoma
- Demyelinating-like disorders
- Congestive heart failure
- Aplastic anemia, pancytopenia, thrombocytopenia, neutropenia, and leucopenia andany
- Serious bleeding events
- Lupus and lupus-like illness
- Serious skin reactions (eg, Stevens Johnson Syndrome, toxic epidermal necrosis, and erythema multiforme)
- A confirmed LTBI must be reported as an AE of interest
- Confirmed active TB is an AE of interest. In the event that an active TB occurrence meets the protocol's SAE criteria, it is also an SAE.

Note: Potential Hy's Law, defined as 3xULN alanine aminotransferase or aspartate aminotransferase with coexisting $\ge 2xULN$ total bilirubin in the absence of $\ge 2xULN$ alkaline phosphatase, with no alternative explanation for the biochemical abnormality, must ALWAYS be reported to UCB as an AE of interest (ie, without waiting for any additional etiologic investigations to have been concluded). Follow-up information should then be reported if an alternative etiology is identified during investigation and monitoring of the subject.

Immediate reporting of adverse events 10.4

The following AEs must be reported immediately:

- SAE: AE that the Investigator classifies as serious by the above definitions regardless of causality
- Suspected transmission of an infectious agent via a medicinal product
- AE of interest (see Section 10.3)

Anticipated serious adverse events

The following list of Anticipated SAEs has been identified, as these events are anticipated to occur in the population studied in this protocol at some frequency that is independent of drug exposure. This original list will remain in effect for the duration of the protocol.

This list does not change the Investigator's obligation to report all SAEs (including Anticipated SAEs) as detailed in Section 10.2.2.

Table 10–1: Anticipated serious adverse events in population independent of drug exposure

Population	Anticipated SAE(s)	
Rheumatoid arthritis ^a	Rheumatoid arthritis	
Crohn's disease ^a	Crohn's disease Perianal abscess Abdominal pain	
Ankylosing spondylitis	Ankylosing spondylitis	

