10.6 Laboratory measurements

Hematology, biochemistry, and urinallysis samples will be taken at Screening, Baseline, Weeks 2, 4, 12, 24, 36, 48, 60, 72, 84, and 96 WD Visit. Testing for HBs-Ag, HBc-Ab, HBs-Ab, HCV-Ab, HIV, and HLA-B27 (if not yet known) will be performed at Screening.

• Hepatitis –associated disease markers

For all subjects, blood samples will be collected by qualified site personnel for the determination of the following:

- HBc-Ab
- HBs-Ag
- HBs-Ab
- HCV-Ab

These samples will be collected at the Screening Visit.

Hepatitis B virus deoxyribonucleic acid and hepatitis C virus ribonucleic acid are available as needed to assess the clinical status of subjects if required during the study.

^a The lists of anticipated SAEs were based on the treatment-emergent SAEs with an incidence ≥0.5% in subjects who participated in UCB Sponsored placebo-controlled studies who received placebo (Crohn's disease and rheumatoid arthritis safety pooling).

The urinalysis will be performed with a dipstick, and in case of a positive outcome, on a clean catch urine sample sent to the central laboratory for analysis. The central laboratory will analyze and assess blood and urine samples for the following:

Table 10–2 lists the laboratory parameters that will be measured:

Table 10–2: Laboratory measurements

Hematology	Chemistry	Urinalysis	Others
Red blood cells	Sodium	рН	Hepatitis B surface antigen
Hemoglobin	Potassium	Protein	Antibodies to hepatitis C
Hematocrit	Chloride	Glucose	Antibodies to HIV
Platelets	Bicarbonate	Blood	HLA-B27
White blood cells	Total calcium	Esterase	
Neutrophils	Inorganic phosphorus	Microscopy (WBC, RBC, casts, crystals, bacteria) (Microscopy will be performed only when there are abnormalities on dipstick)	
Lymphocytes	CRP Glucose Clino		
Monocytes	Glucose		
Eosinophils	Creatinine		
Basophils	Uric acid		
	Urča		
	Total protein		
, 10 3	Albumin		
- Sedio	Alkaline phosphatase		
cannot be use	Aspartate aminotransferase		
Earth	Alanine aminotransferase		
	Bilirubin		
	Total cholesterol		

CRP= C-reactive protein; HIV= human immunodeficiency virus; HLA-B27= human leukocyte antigen B27; RBC=red blood cell; WBC=white blood cell

10.6.1 **Pregnancy testing**

Pregnancy testing must be carried out for women of childbearing potential and will consist of serum testing at Screening, and urine dipstick testing at Baseline, Week 96/WD Visit, and

rnysical assessments

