The following notes to AEs of interest in the clinical study protocol are given for reporting purposes only, and therefore will not be summarized separately: A confirmed LTBI must be reported as an AE of interest. Confirmed active TB is an AE of interest. In the event that an active TB occurrence meets the protocol's SAE criteria, it is also an SAE. Potential Hy's Law, defined as $\geq 3 \times \text{ULN}$ alanine aminotransferase or aspartate aminotransferase with coexisting $\geq 2 \times \text{ULN}$ total bilirubin in the absence of $\geq 2 \times \text{ULN}$ alkaline phosphatase, with no alternative explanation for the biochemical abnormality is also considered an AE of interest.

The following events are not officially considered to be AEs of interest but are nonetheless considered to be interesting enough to be summarized in stand-alone tables: 1) Hepatic events and 2) Hypersensitivity reactions and anaphylactic reactions.

The approach for summarizing AEs of interest is detailed in the

UCB AE of interest program specifications for Cimzia from 18 June 2018.

Data collected on hospitalization will be presented in a listing.

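### The Hy's Law subject count in SAP section 10.3 omits the alkaline phosphatase condition that SAP section 10.2 and Protocol section 10.3 both include

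*SAP*

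**What the plan says.** Three places in the current text define this event.

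- **SAP section 10.3 (Clinical laboratory evaluations)** introduces a subject count: "The number of subjects meeting the criteria for Hy's Law is of particular importance". The criteria are a bilirubin limit of at least 2 x ULN together with an ALT or AST limit: "elevation of Bilirubin and 3 x ULN elevation of either ALT or AST". One further condition follows: "In order to meet the above criteria, a subject must experience the elevation in bilirubin and ALT or AST at the same visit". ALP is not part of the rule. It appears in that section only as a separate markedly abnormal flag, at more than 3 x ULN.
- **SAP section 10.2 (Adverse events)** defines potential Hy's Law as ALT or AST at or above 3 x ULN with total bilirubin at or above 2 x ULN, but only where there is no elevation to 2 x ULN or more of "alkaline phosphatase, with no alternative explanation for the biochemical abnormality is also considered an AE of interest". The same paragraph says that these notes "are given for reporting purposes only, and therefore will not be summarized separately".
- **Protocol section 10.3 (Adverse events of interest)** has the same structure. It requires the ALT/AST limit and at least 2 x ULN "total bilirubin in the absence of" an ALP elevation of 2 x ULN or more, and makes such cases immediately reportable: "alkaline phosphatase, with no alternative explanation for the biochemical abnormality, must ALWAYS be reported to UCB as an AE of interest".

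ALP is on the chemistry list in Protocol Table 10-2 ("Alkaline phosphatase"), alongside ALT, AST and bilirubin.

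**The concern.** Consecutive sections of the SAP attach the same name to two different rules. The wider rule governs the only Hy's Law subject count that the SAP specifies, because section 10.2 gives potential Hy's Law no summary of its own. A programmer following section 10.3 would count a subject whom the trial's own definition excludes.

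The other planned summaries would not reliably expose this. The ALP flag starts above 3 x ULN, so ALP between 2 and 3 x ULN goes unflagged, and the shift tables show only low, normal and high. A reader would have to look up ALP in the by-subject listings.

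At stake is the meaning of a safety figure that the SAP itself marks out. Sites report the event under the protocol's definition, while the laboratory count uses another.

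**Working it through.** No sample size, power or alpha figure depends on this point, so there is no stated figure to reproduce. The check sets the definitions side by side.

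| Condition | Protocol 10.3 | SAP 10.2 | SAP 10.3 |
|---|---|---|---|
| ALT or AST | 3 x ULN (sign: see below) | at least 3 x ULN | 3 x ULN, no sign |
| Total bilirubin | at least 2 x ULN | at least 2 x ULN | at least 2 x ULN |
| ALP at or above 2 x ULN | excludes the case | excludes the case | not mentioned |
| No other explanation | required | required | not mentioned |
| Timing | coexisting | coexisting | same visit |

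**Direction of the difference.** Take one reading of the ALT/AST limit and apply it to both rules. Let W be the subjects who meet the ALT/AST and bilirubin limits at some visit, and N those who do so at a visit where ALP is also below 2 x ULN. Every member of N is in W, so

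count(W) − count(N) = number of subjects whose every qualifying visit has ALP at or above 2 x ULN, which is zero or more.

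**Illustrative subjects (assumed values, one visit each):**

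1. ALT 4 x, bilirubin 3 x, ALP 5 x ULN. Counted under SAP 10.3; excluded under SAP 10.2 and Protocol 10.3. The separate ALP flag is raised.
2. The same, with ALP between 2 and 3 x ULN. Counted under SAP 10.3; excluded under the other two. No ALP flag is raised.
3. The same, with ALP below 2 x ULN. Counted under SAP 10.3 and meets the laboratory part of the other two. Whether it is a potential Hy's Law case then turns on the clinical judgment about other explanations.

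**Size.** One subject of type 1 or 2 among the planned 86 is 1/86 = 0.0116, or 1.2%. The documents give no rate for such events, so the expected difference cannot be derived.

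**The missing sign.** In SAP 10.3 the ALT/AST limit appears twice without a sign, each time in the same sentence as a bilirubin limit that has one. Section 10.3 flags ALT and AST at more than 3 x ULN, while section 10.2 uses at least 3 x ULN. A value of exactly 3 x ULN is therefore undetermined. Protocol 10.3 also shows no sign in the available text, but the Amendment 2 listing prints the same sentence with it. The protocol's sign was probably lost when the text was read from PDF, and it is not counted here as a discrepancy.

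**The case against.** The strongest reply is that nothing important depends on this count. It is descriptive, no hypothesis or stopping rule uses it, and leaving out ALP can only add subjects, never hide one. SAP section 3.1 puts all data into by-subject listings, SAP section 10.2 gives hepatic events their own table, and ALP above 3 x ULN is flagged separately. Protocol section 6.2 also excludes subjects with liver function tests above 2.0 x ULN at Screening. All of that stands, and it limits the consequence. It does not make the label correct.

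Two stronger readings are tempting, and the documents do not support them.

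- A reader might infer that two Hy's Law tables will show different numbers. SAP section 10.2 plans no separate summary, and section 10.3 specifies a count without naming a table. The conflict lies between the laboratory count and the adverse-event-of-interest definition that sites use for reporting.
- A reader might infer an undeclared departure that belongs in SAP section 3.9. That section lists changes to protocol-defined analyses. Protocol section 12.4 defines no Hy's Law analysis and leaves the laboratory details to the SAP, while Protocol section 10.3 is a reporting rule. The absence from section 3.9 is therefore weak evidence of anything.

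**Conclusion.** The inconsistency is real and in current text. As written, SAP section 10.3 can count subjects under the name Hy's Law whom SAP section 10.2 and Protocol section 10.3 exclude. For a common ALT/AST limit the error runs in one direction, upwards.

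Its size is small and may be nil. The reported number changes only if a subject meets the ALT/AST and bilirubin limits at the same visit with ALP at or above 2 x ULN. It would be wrong to infer that such subjects will certainly be counted, since both rules may give zero. The 1.2% figure is what one case would represent, not a forecast. The primary analysis, alpha and sample size are unaffected.

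Nor should a reader infer that adding ALP makes the count identical to the adverse-event definition. The condition on other explanations cannot be read from laboratory data, so a biochemical count remains wider on that point.

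The conclusion assumes that section 10.3 will be programmed as it reads and that no separate specification supplies the ALP condition. It merits a correction because the SAP gives this count particular weight and the remedy is simple.

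**What to change.** In SAP section 10.3, define the row as: *potential Hy's Law (laboratory criteria): ALT or AST ≥3 x ULN and total bilirubin ≥2 x ULN with ALP <2 x ULN, all at the same visit*. Keep the existing same-visit rule, since that section's handling of repeat and additional samples is built around visits. Add a note that the absence of another explanation is judged clinically and is not applied in the laboratory count.

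If the broader screen is wanted as well, show it as a separate row labelled as ALT/AST and bilirubin elevation regardless of ALP, and not as Hy's Law.

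The cost is a short change of SAP wording and one programming condition, plus one more row if the screen is kept. No new data are needed.

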10.4 Vital signs, physical findings, and other observations related to safety

10.4.1 Vital signs

The changes from Baseline in vital signs will be analyzed over time in the SS for observed cases. In addition, the last value (end of treatment) during treatment will be analyzed. End of treatment will be defined as last visit not including the Follow-up visit. Early Withdrawal Visits will be assigned to what would have been the next scheduled visit. The following vital signs measurements will be assessed:

- Pulse rate (bpm)
- Systolic blood pressure (mmHg)
- Diastolic blood pressure (mmHg)
- Body temperature (°C)

Additionally, body weight (kg) will also be presented together with vital signs.

10.4.2 Pregnancy testing

Pregnancy testing must be carried out for women of childbearing potential and will consist of serum testing at Screening, and urine dipstick testing at Baseline, Week 96/WD Visit, and FU Visit. No tables will be generated and data listed only.

10.4.3 Physical assessments

A physical examination will be performed at Screening, Baseline, Weeks 2, 4, 12, 24, 36, 48, 60, 72, 84, 96/WD Visit, and at the FU Visit. Physical examination findings will be recorded in the eCRF only at Screening. Physical examination data will be listed only.

10.4.4 MRI assessments

Magnetic resonance imaging of the SIJs will be performed at the Screening Visit only. An MRI performed ≤ 3 months prior to the Baseline Visit may be used as the Baseline. The data will be presented in a listing only.

10.4.5 Tuberculosis assessments

The interferon-gamma release assay (IGRA) test will be done by the central laboratory. The test results will be reported as positive, negative, or indeterminate and must be reviewed by an experienced TB specialist, radiologist, or a pulmonologist. The test result data, the data about history of latent tuberculosis, as well as the TB questionnaire result data, including the 2 questions [REDACTED]

[REDACTED] will be presented in listings.

10.4.6 Chest x-ray

Screening chest x-ray must have occurred within 3 months prior to Screening Visit and should be repeated only if the TB test was confirmed positive or any further evidence is suggestive of potential TB infection. Additional chest x-ray or other imaging test should be performed when positive signs and symptoms indicate pulmonary infection, including potential TB infection, or when close exposure to persons with TB is documented. The data collected on chest x-ray will not be tabulated, but presented in a listing.

This document cannot be used to support any marketing authorization application and any extensions or variations thereof.

REDACTED COPY

12 APPENDICES

12.1 APPENDIX 1: Compliance Ratio Calculation

The general formula for treatment compliance is given as follows:

$$CR = \frac{T_{Dur_stu} - \Delta_{Cum}}{T_{Dur_stu}}$$

where T_{Dur_stu} is the study duration and Δ_{Cum} is the cumulative difference between actual and scheduled day of administration. The CRD ranges between 0 and 1.

There are 2 methods to determine the CR. CR (1) is based upon scheduled days which reference the Baseline visits. CR (2) is based upon scheduled days which reference the previous dosing administration date. CR (1) and CR (2) each will be computed separately. The definition of study duration and cumulative difference varies for the 2 calculations. In all cases, if the subject was randomized, but study drug was never administered then the CR is equal to 0. The CR is limited to a range of 0 to 1. Therefore, if for any reason a negative value is computed, the CR must be set to 0. Specific details for each calculation follow.

CR(1):

$$T_{Dur_stu} = Date_{Last} - Date_{BL}$$

$$\Delta_{Cum} = \sum_i |(AD_i - SD_i)|$$

where $i = \text{Week } 0, 2, 4, 6, \dots, XX$

$AD_i = \text{Actual day of administration, for Week } i=0 \text{ to } XX \text{ by } 2$
 $SD_i = (i/2) \times 14,$ for Week $i=0 \text{ to } XX \text{ by } 2$

Note: XX represents the last completed visit in which study drug should have been administered. If subject is still in the study but AD_i is missing, then $ABS[AD_i - SD_i]=14$ for the missed Visit i .

CR(2):

$$T_{Dur_stu} = Date_{Last} - Date_{BL}$$

$$\Delta_{Cum} = \sum_i |(AD_i - SD_i)|$$

where $i = \text{Week } 0, 2, 4, 6, \dots, XX$

$AD_i = \text{Actual day of administration, for Week } i=0 \text{ to } XX \text{ by } 2$
 $SD_i = \{0,$ for Week $i=0$ }
 $\{14 + AD_{i-2},$ for Week $i=2 \text{ to } XX \text{ by } 2$ }

Note: XX represents the last completed visit in which study drug should have been administered. If subject is still in the study but AD_i is missing, then $ABS(AD_i - SD_i)=14$ for the missed Visit i .

Example

Week	Scheduled day (1)	Scheduled day (2)	Actual day	ABS Diff (1)	ABS Diff (2)
0	0	0	0	0	0
2	14	14	13	1	1
4	28	27	29	1	2
6	42	43	-	14	14
8	56	57	55	1	2
10	70	69	69	1	0
Total	-	-	-	18	19
CR				66/84 = 0.79	65/84 = 0.77

Note that this example is for a 12 week study.

This document cannot be used to support any marketing authorization application and any extensions or variations thereof.
 REDACTED COPY

13 AMENDMENT(S) TO THE STATISTICAL ANALYSIS PLAN (SAP) (IF APPLICABLE)

13.1 AMENDMENT 1

Rationale for the amendment

This SAP was amended after the Data Evaluation Meeting, in order to include the handling of AU flares if the time interval between 2 subsequent flares is less than 3 months. The corresponding derivations for the analysis of the primary efficacy variable, including imputation of start and end dates of flares, have been added. In addition, the interim analysis will include data up to Week 48 only. And according to the most recent AE of interest guidance, separate tables for demyelinating disorders and congestive heart failures were included.

Modifications and changes

Changes in section 4.2

Following has been added at the end of section 4.2:

Efficacy variables

The start and end dates of flares will be imputed for the analyses of AU flares data, in order to allow the calculation of time intervals between 2 consecutive flares and the duration of flares. Different rules will be applied for pre-study and on-study period flares.

Pre-study period (12 months prior to Baseline, i.e. 365 days prior to Baseline, until Baseline):

- Missing start day, but month and year present: Impute the first day of the month unless one of the following conditions apply:
 - Month and year are the same as month and year of the start date of pre-study period, then impute with the start date of pre-study period.
 - Month and year are the same as month and year of the end date of previous flare, and the end date is clearly greater than end date of previous flare, then impute with the end date of previous flare.
 - In the case that month and year of the start date of pre-study period is the same month and year of the end date of previous flare, then use the latest date of both for imputation.
- Missing start day and month, but year present: Impute January 1st unless one of the following conditions apply:
 - Year is the same as year of the start date of pre-study period, then impute with the start date of pre-study period.
 - Year is the same as year of the end date of previous flare, then impute with the end date of previous flare.
 - In the case that year of the start date of pre-study period is the same year of the end date of previous flare, then use the latest date of both for imputation.

- Completely missing start dates of flares will only be imputed if it is clear based on the end date that the flare occurred within 12 months prior to treatment start. Then the maximum (latest) of start date of pre-study period and end date of previous flare will be considered.
- Missing end day, but month and year present: Impute the last day of the month unless one of the following conditions apply:
 - Month and year are the same as month and year of the end date of pre-study period, then impute with the end date of pre-study period.
 - Month and year are the same as month and year of the start date of subsequent pre-study flare before Baseline, then impute with the start date of subsequent pre-study flare.
 - In the case that month and year of the end date of pre-study period is the same month and year of the start date of subsequent pre-study flare, then use the earliest date of both for imputation.
- Missing end day and month, but year present: Impute December 31st unless one of the following conditions apply:
 - Year is the same as year of the end date of pre-study period, then impute with the end date of pre-study period.
 - Year is the same as year of the start date of subsequent pre-study flare, then impute with the start date of subsequent pre-study flare.
 - In the case that year of the end date of pre-study period is the same year of the start date of subsequent pre-study flare, then use the earliest date of both for imputation.
- Completely missing end dates of flares will only be imputed if it is clear based on the start date that the flare occurred within 12 months prior to treatment start. Then the minimum (earliest) of end date of pre-study period and start date of subsequent pre-study flare will be considered.

On-study period (Baseline until end of treatment):

- Missing start day, but month and year present: Impute the first day of the month unless one of the following conditions apply:
 - Month and year are the same as month and year of the start date of study medication, then impute with the start date of study medication.
 - Month and year are the same as month and year of the end date of previous on-study flare, and the end date is clearly greater than end date of previous on-study flare, then impute with the end date of previous on-study flare.
 - In the case that month and year of the start date of study medication is the same month and year of the end date of previous on-study flare, then use the latest date of both for imputation.
- Missing start day and month, but year present: Impute January 1st unless one of the following conditions apply:

- Year is the same as year of the start date of study medication, then impute with the start date of study medication.
- Year is the same as year of the end date of previous on-study flare, then impute with the end date of previous on-study flare.
- In the case that year of the start date of study medication is the same year of the end date of previous on-study flare, then use the latest date of both for imputation.
- Completely missing start dates of flares will only be imputed if it is clear based on the end date that the flare occurred after treatment start during the on-study period. Then the maximum (latest) of start date of study medication and end date of previous on-study flare will be considered.
- Missing end day, but month and year present: Impute the last day of the month unless one of the following conditions apply:
 - Month and year are the same as month and year of the end date of on-study period, then impute with the end date of on-study period.
 - Month and year are the same as month and year of the start date of subsequent on-study flare, then impute with the start date of subsequent on-study flare.
 - In the case that month and year of the end date of on-study period is the same month and year of the start date of subsequent on-study flare, then use the earliest date of both for imputation.
- Missing end day and month, but year present: Impute December 31st unless one of the following conditions apply:
 - Year is the same as year of the end date of on-study period, then impute with the end date of on-study period.
 - Year is the same as year of the start date of subsequent on-study flare, then impute with the start date of subsequent on-study flare.
 - In the case that year of the end date of on-study period is the same year of the start date of subsequent on-study flare, then use the earliest date of both for imputation.
- Completely missing end dates of flares will only be imputed if it is clear based on the start date that the flare occurred after treatment start during the on-study period. Then the minimum (earliest) of end date of on-study period and start date of subsequent on-study flare will be considered.

Changes in section 4.3 (third paragraph)

An interim analysis is planned to be conducted after the last subject has completed the Week 48 assessment. That is when each treated subject has completed the Week 48 Visit, or withdrawn prematurely. All data collected until the database cut-off date will be included. With this interim analysis, first study results will be available already about one year before the final analysis of the study. There is no intention to stop the study early for efficacy or for futility. The interim summaries and listings will be based on the same shells as for the final analysis, unless otherwise stated. The interim listings will include all data collected so far, and also display data after Week

48 if available. The summary tables presenting results by visit will only consider results up to Week 48 Visit for the interim analysis. Summary tables of results not provided by visit, e.g. adverse events, concomitant medication, will consist of all the data collected so far at the interim cut-off. All AU flares will be counted for a subject, irrespective of whether a subject has only 48 weeks of data or already more weeks of data collected.

Has been changed to:

An interim analysis is planned to be conducted after the last subject has completed the Week 48 assessment. That is when each treated subject has completed the Week 48 Visit, or withdrawn prematurely. All data collected until the database cut-off date will be included. With this interim analysis, first study results will be available already about one year before the final analysis of the study. There is no intention to stop the study early for efficacy or for futility. The interim summaries and listings will be based on the same shells as for the final analysis, unless otherwise stated. The interim listings will include all data collected **up to** Week 48. The summary tables presenting results by visit will only consider results up to Week 48 Visit for the interim analysis. Summary tables of results not provided by visit, e.g. adverse events, concomitant medication, will **not include events or medication that started after the Week 48 Visit. Data collected after Week 48 will not be presented in the interim analysis.**

Changes in section 6.2 (second paragraph)

Time since onset of first uveitis flare will be calculated as the difference between the date of Baseline visit and the onset date of first uveitis flare. If the onset date of first uveitis flare is partial, it will be imputed to the most recent feasible date (ie, last day of the month if only day is missing, or the last day of the year if day and month are missing). Time since onset of first uveitis flare will be summarized as continuous variable in days, as well as categorized into <2 years and ≥ 2 years.

Has been changed to:

Time since onset of first uveitis flare will be calculated as the difference between the date of Baseline visit and the onset date of first uveitis flare. If the onset date of first uveitis flare is partial, it will be imputed to the **first** feasible date (ie, **first** day of the month if only day is missing, or the **first** day of the year if day and month are missing). Time since onset of first uveitis flare will be summarized as continuous variable in days, as well as categorized into <2 years and ≥ 2 years.

Changes in section 8.1.1

The primary efficacy variable is the number of distinct episodes of AU flares in the Treatment Period. Pre-study and on-study AU flare episodes will be counted. An episode of AU flares is considered as pre-study, if the start date of flare is before the start date of study medication. An episode of AU flares is considered on-study, if the start date of flare is on or after the start date of study medication.

The log-time offset in the Poisson model will consist of the length of pre-study and on-study reporting periods in days. As the documentation of pre-study episodes starts 12 months prior to Baseline, the pre-study period length for offset is 365 days for each subject. The on-study period length for offset is the time in days from start of study medication until last visit.

Disease duration of axSpA, which will be included in the Poisson model as a factor, is calculated from the start date of first AU flare episode until the Baseline visit date, and is categorized into <2 years and ≥ 2 years.

Has been changed to:

The primary efficacy variable is the number of distinct episodes of AU flares in the Treatment Period. **Per protocol, a flare is considered a new episode if a gap of at least 3 months occurs between 2 flares. If AU flare episodes as reported by the investigator occur less than 3 months (90 days) apart in the same eye, these will programmatically corrected, such that a new AU flare within 3 months (90 days) after the end of the previous AU flare in the same eye will be considered as pertaining to the same AU episode. These flares will then be counted as one episode. Otherwise, if the time interval between 2 consecutive AU flares is greater than 3 months (90 days), or a separate eye is affected, the AU flares will be considered as separate episodes.**

Pre-study and on-study AU flare episodes will be counted. An episode of AU flares is considered as pre-study, if the start date of flare is before the start date of study medication **and if the flare occurs within the 12 months (365 days) prior to the start of study medication.** An episode of AU flares is considered on-study, if the start date of flare is on or after the start date of study medication. **Pre-study and on-study flares of the same eye will be combined if the time interval between the end of pre-study flare and the start of subsequent on-study flare is less than 3 months (90 days). The resulting flare episode will be considered as pre-study flare episode.**

The log-time offset in the Poisson model will consist of the length of pre-study and on-study reporting periods in days. As the documentation of pre-study episodes starts 12 months prior to Baseline, the pre-study period length for offset is 365 days for each subject. The on-study period length for offset is the time in days from start of study medication until last visit.

Disease duration of axSpA, which will be included in the Poisson model as a factor, is calculated from the start date of first AU flare episode until the Baseline visit date, and is categorized into <2 years and ≥ 2 years.

Changes in section 8.1.2

The primary efficacy analysis will be repeated in the subgroup of subjects with at least 1 documented AU flare within 12 months prior to Baseline.

The AU flare rate (event rate) per 100 patient-years of exposure, both before and during the study will be calculated. The corresponding rate ratio along with 95% confidence interval (Garwood, 1936) will be presented as a key supportive analysis to the primary efficacy analysis results (see [Section 8.2.1](#)).

Has been changed to:

The primary efficacy analysis will be repeated in the subgroup of subjects with at least 1 documented AU flare within 12 months prior to Baseline.

The AU flares as reported by the investigators, without programmatically correcting for the 3 month interval between 2 flares, will be analyzed in addition to the primary efficacy variable of protocol-defined AU flares at least 3 months apart.

The AU flare rate (event rate) per 100 patient-years of exposure, both before and during the study will be calculated. The corresponding rate ratio along with 95% confidence interval (Garwood, 1936) will be presented as a key supportive analysis to the primary efficacy analysis results (see [Section 8.2.1](#)).

Changes in section 8.2.2 (last paragraph)

The variables related to ASDAS clinical improvement are defined as follows:

- ASDAS-Clinically Important Improvement (ASDAS-CII): ASDAS reduction (improvement) of ≥ 1.1 relative to Baseline
- ASDAS-Major Improvement (ASDAS-MI): ASDAS reduction (improvement) of ≥ 2.0 relative to Baseline

Change from Baseline in ASDAS at Week 48 and Week 96 are secondary efficacy variables.

Has been changed to:

The variables related to ASDAS clinical improvement are defined as follows:

- **ASDAS- Clinical Improvement (ASDAS-CI): ASDAS reduction (improvement) of >0 relative to Baseline**
- ASDAS-Clinically Important Improvement (ASDAS-CII): ASDAS reduction (improvement) of ≥ 1.1 relative to Baseline
- ASDAS-Major Improvement (ASDAS-MI): ASDAS reduction (improvement) of ≥ 2.0 relative to Baseline **or has the lowest score possible post-baseline (i.e. when CRP<LLOQ and all other components are 0, then the minimum ASDAS score is 0.636 to 3 decimal places).**

Change from Baseline in ASDAS at Week 48 and Week 96 are secondary efficacy variables.

Changes in section 10.2

AEs of interest will be summarized. The following AEs of interest will be summarized in stand-alone tables:

- Opportunistic infections
- Malignant and unspecified tumors
- Malignant tumors
- Serious cardiovascular events
- Aplastic anemia, pancytopenia, thrombocytopenia, neutropenia, and leucopenia
- Serious bleeding events

